- ii. Evaluate if there is a significant difference in operative duration (time) and intra-operative cost for patients undergoing EGD vs.
 ViSiGi® 3D suction device calibration during sleeve gastrectomy
- iii. Assess longer post-operative outcomes including GERD symptom severity and weight loss
 - 1. GERD-HRQL questionnaire pre-op and post-op 2 (+/- 2 months) & 12 mo (+/- 12 months) (4)
 - 2. Weight loss mean % total body weight loss, mean % EWL, mean % change in BMI (12 mo, +/- 12 months)

3. Background

Previous studies have shown that compared to a standard weighted rubber bougie (RB), using a suction calibration device (SCD) results in a straighter staple line compared to a twisted and corkscrewed staple line (1); no studies to date have compared upper endoscopy calibration to SCD for SG. Due to the straighter, and therefore shorter, staple line, the hypothesis is the surgeon should be able to use fewer staple loads with a SCD. Bariatric staple loads are expensive, so a reduction in their use has the potential for savings to the hospital.

The study will also look at how a suction calibration system can create savings for the hospital in OR time and scope processing costs. As previously mentioned, the SCD may require fewer stapler load firings; it also eliminates the need for placing multiple tubes in to the stomach as well as an upper endoscopy leak test and therefore saves the OR staff time and may decrease operative duration. The SCD is also disposable which

eliminates the need for reprocessing. Current estimates for reprocessing an endoscope are around \$200 (2) thus the SCD use may decrease operative cost.

It is also hypothesized that a misaligned smaller sleeve after a LSG procedure can increase the prevalence of post-operative GERD due to removal of the fundus and twisting of the sleeve (3). A straighter, correctly calibrated sleeve should decrease the prevalence of GERD in patients. Therefore, the study will also look at the prevalence of pre-operative vs. post-operative GERD symptoms in patients who are undergoing LSG with endoscopic calibration vs. SCD.

4. Study Intervention/Investigational Agent

	Pre-operative period & Bariatrical Surgical consult	Day of Surgery (LSG)	Immediate Post-op follow-up (3 weeks) (+/- 2 weeks)	2mo post op f/u (+/- 2 months)	12 mo post op f/u (+/- 12 months)

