- Risks/discomforts of EGD and ViSiGi device are comparable. Using a ViSiGi device is similar to both a standard weighted bougie and an EGD calibration technique. The ViSiGi device is similar to a gastroscope in that they both have suction, calibration, and leak testing capabilities. The benefit of the ViSiGi device is that it obviates the need for doing an EGD during sleeve gastrectomy, is single patient use and thus does not require reprocessing, and doesn't require a scope tower to operate it. Potential benefits of using the ViSiGi device (in lieu of endoscopic calibration) in order of highest probability are as follows: 1) less staple loads, 2) shorter OR time, 3) reduced cost, 4) decreased post-op GERD rates.
- Data analyst and study coordinator to have research roles at this time
- Immediate post-op follow-up 3 weeks after surgery (+/- 2 weeks) to 12 months out (+/- 12 months)
 - Assessments made by surgeon will be for diagnostic, therapeutic and research purposes as appropriate
 - Study coordinator and data analyst will function in research roles only
 - Goal in this period is predominantly research purposes only
 - Due to constraints from COVID-19 and decreased in-person follow-up, the 12-month assessment time frame will be extended to 24 months post-surgery to help gather GERD-HRQL and weight loss data
 - a. What type of information will be collected:
 - i. See above table
 - ii. Demographic and clinical variables will be collected at (baseline) including age, gender, race, BMI, smoking status, functional status, and medical comorbidities:
 - 1. EHR
 - 2. MBSAQIP
 - 3. Baseline GERD-HRQL scores (standardized questionnaire)
 - iii. Intra-operative/procedure data (i.e. type of stapler used, # staple load firings, length and color stapler loads, etc.)
 - 1. EHR
 - 2. Research data sheets
 - iv. Post-operative data & assessment
 - 1. EHR
 - 2. MBSAQIP (30-day outcomes and weight loss outcomes)
 - 3. Cost data (administrative data) from internal databases
 - 4. GERD-HRQL scores (standardized questionnaire)

6. Inclusion and Exclusion Criteria

Patients selected for this study will be adults, 18 years old or older, who have already agreed with their surgeon that LSG is the best choice for them. Patients will be excluded by the following criteria;

- Subjects with prior gastric surgery or bariatric surgery (including prior adjustable gastric band and/or sleeve gastrectomy).
- Concomitant hiatal surgery
- Paraesophageal hernia at time of surgery

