There will be 50 patients undergoing LSG with an endoscope and 50 patients undergoing LSG with a suction calibration system. Both methods are clinically accepted and approved methods of performing the procedure. The target enrollment will be 125 to account for attrition due to screen failures, early withdrawals, etc. For this study we use a randomized block design (RBD) to assign participants to one of two sleeve groups. In a RBD we divide participants into subgroups called blocks (e.g. gender, race, etc.), such that the variability within blocks is less than the variability between blocks. Then, subjects within each block are randomly assigned to treatment conditions (i.e. SG with EGD or SG with ViSiGi device). The purpose of the RBD is to help reduce variability within treatment conditions and potential confounding from blocking factors, producing a better estimate of treatment effects. We are adequately powered to detect a mean difference in stapler load firings of 0.4 between groups assuming a standard deviation of 0.7, which is consistent with our institutional sleeve gastrectomy experience. After all cases have been performed statistical methods will be implemented to determine any difference in outcomes. An initial approach will focus on a pairwise analysis (t-test) between the ViSiGi and EGD calibration groups for each of the primary and secondary aims. A more comprehensive multivariate analysis factoring in demographic and clinical variables will be performed to further delineate significant differences in the 2 sleeve gastrectomy methods. In the unlikely situation that an adverse event occurs, the event will be inspected to determine if an early stoppage is necessary.

14. Provisions to Monitor the Data to Ensure the Safety of Participants

All methods used in this study for performing sleeve gastrectomy are already approved and clinically accepted. Validated users of the device will be attending surgeons who have been trained using the ViSiGi device via online video-based education

(https://www.youtube.com/watch?v=zDhc-1fr32E), review of the manufacturer instructions for use (IFU) sheet below:

(chromeextension://oemmndcbldboiebfnladdacbdfmadadm/https://www.boehringerlabs.com/wp-content/uploads/2018/09/5232009.pdf) as well as in-person education via representatives from Boehringer Laboratories, LLC.

All surgeons will be required to complete the video-based module and review the IFU sheet prior to using the ViSiGi device.

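### The main GERD comparison should be one baseline-adjusted ANCOVA at one named time point, not the unadjusted t-test planned in Section 13

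*Combined protocol and SAP*

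**What the plan says.** Section 13 (Statistical Analysis) does not mention GERD by name. It covers every aim with an initial "pairwise analysis (t-test) between the ViSiGi and EGD calibration groups for each of the primary and secondary aims", and then says: "A more comprehensive multivariate analysis factoring in demographic and clinical variables will be performed". It lists no covariates for that second step.

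The GERD outcome has to be pieced together from other sections:

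- **Form.** Secondary aim iii in Section 2 is to "Assess longer post-operative outcomes including GERD symptom severity and weight loss". Section 3 (Background) says that "the study will also look at the prevalence of pre-operative vs. post-operative GERD symptoms in patients", and the list of possible device benefits in Section 5 includes "decreased post-op GERD rates". No cut-off defining prevalence is given.
- **Times.** Section 2 specifies the "GERD-HRQL questionnaire pre-op and post-op 2 (+/- 2 months) & 12 mo (+/- 12 months"). Section 5 adds: "Due to constraints from COVID-19 and decreased in-person follow-up, the 12-month assessment time frame will be extended to 24 months post-surgery". The synopsis sets individual study duration at 12 months for patients consented before 05/10/2021 and not reconsented, and at 24 months for the others.
- **Baseline.** Section 5 lists "Baseline GERD-HRQL scores (standardized questionnaire") among the baseline variables. The synopsis places this questionnaire on the day of operation. The Section 4 table and Section 5 place it in the pre-operative consult period.

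**The concern.** GERD-HRQL is reported by patients who know their arm, and less GERD is one of the benefits hoped for from the device. Such an outcome needs its analysis fixed beforehand. The planned t-test also ignores a baseline score that the trial already collects, so it gives up precision for nothing.

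Follow-up score or change, early or late time point, and adjusted or unadjusted model are all left open. The GERD result could therefore be settled after the data are seen. Even a named time point would not be enough as the windows stand, because a questionnaire completed at month 3 qualifies for both.

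ANCOVA also works best with a baseline that knowledge of the arm cannot have influenced, so the conflicting statements about its timing matter here.

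**Working it through.** **1. The plan's own figure.** Section 13 gives 50 per arm, a difference of 0.4 stapler firings and an SD of 0.7. It states neither alpha nor power, so take two-sided 0.05 and 80%:

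n per arm = 2 × (1.960 + 0.842)² × 0.7² / 0.4² = 2 × 7.85 × 3.0625 = 48.1, so 49.

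Fifty per arm gives 81.5% power (normal approximation) or 80.8% (t-based). Enrolling 125 allows for 20% loss: 125 × 0.80 = 100. The figure reproduces, but it concerns stapler firings only. The documents give no GERD effect, SD or baseline correlation, so what follows is in SD units of the follow-up score over a range of assumed correlations.

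**2. Windows.** 2 ± 2 gives 0 to 4 months and 12 ± 12 gives 0 to 24 months. The first lies wholly inside the second.

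**3. Variance.** Let ρ be the correlation between baseline and follow-up, and k the ratio of post-operative to pre-operative SD. Relative to the follow-up score alone (variance 1):

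- change score: 1 + 1/k² − 2ρ/k
- ANCOVA: 1 − ρ²

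Change minus ANCOVA equals (1/k − ρ)², which is never negative. Apart from the degree of freedom spent on the covariate, ANCOVA is at least as precise as either t-test, whatever ρ and k are.

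| | ρ = 0.3 | ρ = 0.5 | ρ = 0.7 |
|---|---|---|---|
| ANCOVA variance | 0.91 | 0.75 | 0.51 |
| Cut against follow-up t-test | 9% | 25% | 49% |
| Change-score variance, k = 1 | 1.40 | 1.00 | 0.60 |
| ANCOVA cut against change, k = 1 | 35% | 25% | 15% |
| ANCOVA cut against change, k = 0.7 | 58% | 53% | 51% |
| ANCOVA cut against change, k = 1.4 | 16% | 6% | 0% |

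**4. Detectable difference at 80% power** (two-sided 0.05, noncentral t). ANCOVA multiplies the follow-up figure by √(1 − ρ²), which is 0.954, 0.866 or 0.714.

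| Per arm | Follow-up t-test | ANCOVA, ρ = 0.3 | ρ = 0.5 | ρ = 0.7 |
|---|---|---|---|---|
| 50 | 0.566 | 0.540 | 0.490 | 0.404 |
| 40 | 0.634 | 0.605 | 0.549 | 0.453 |
| 30 | 0.736 | 0.702 | 0.637 | 0.525 |

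For an assumed true difference of 0.5 SD at 50 per arm, power is 69.7% with the follow-up t-test, and 73.7%, 81.5% or 93.4% with ANCOVA.

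**5. Cost of choosing afterwards.** Null trials were simulated (20,000 per ρ, 50 per arm, the same correlation among all three times). The chance of a nominally significant GERD result, over the three values of ρ, was:

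- one named ANCOVA: 4.8% to 5.2%
- better of follow-up and change, one time point: 8.9% to 9.6%
- the same, both time points: 16.1% to 16.2%
- ANCOVA added as a further option: 16.8% to 17.6%

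These figures suppose that the most favourable result is always the one reported.

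**6. Baseline timing.** The synopsis says the day of operation. The Section 4 table and Section 5 say the consult period, which Section 5 puts usually 1 to 2 months before surgery. Section 5 has patients learning their arm before the operation, and Section 16 has them told around the time of it. Section 16 ties consent, but not the questionnaire, to a point before randomisation. No sentence fixes the order of questionnaire and disclosure.

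**The case against.** **The plan is not silent on adjustment.** A reader might infer that baseline GERD is never taken into account. That goes too far: the later multivariate analysis could include it, since Section 5 lists it with the other baseline variables. What stands is that it is not named and is not part of the main comparison.

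**The form is less open than it looks.** A reader might infer that the trial means to test prevalence. Aim iii speaks of severity, and a t-test suits a score. Prevalence and rates appear only in the rationale and the list of benefits. This stands, so prevalence is a side issue here. The choice between follow-up score and change remains open.

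**The baseline may be clean.** A reader might infer that it was taken after patients knew their arm. The documents do not establish this. If the questionnaire is given at the consult and the arm disclosed near surgery, baseline would usually come first. A baseline on the operative day could come after disclosure. That is possible, and a reason to reconcile the text.

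**ANCOVA is partly preference.** A baseline-adjusted repeated-measures model with one named contrast would serve equally well. This is accepted. The case is for one pre-specified, baseline-adjusted comparison.

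**The figures are assumed, and the aim is secondary and unpowered.** Both are true. The direction does not depend on the assumed correlation; the size does. Nothing in the documents shows an intention to select results, so the false-positive figures mark what the wording permits under the least favourable use.

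**Conclusion.** The concern holds as a free improvement to a secondary analysis. The planned t-test is less efficient than an adjustment the trial can already make. The gain is small at a correlation of 0.3 (9% of the variance) and large at 0.7 (49%). Fixing one comparison also holds the false-positive rate for GERD at the nominal 5%, against about 16% to 18% if form, time point and model were picked for the most favourable result.

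Naming 12 months is not enough while its window contains the whole of the earlier one and maximum follow-up differs by consent cohort. The sizes rest on assumed correlations, 50 analysed per arm and two-sided 0.05. The primary endpoint and its sample size are unaffected. The change should be made, but the trial does not stand or fall by it.

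**What to change.** Before any comparison by arm:

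1. In Section 13, replace the t-test as the main GERD comparison with one ANCOVA of the GERD-HRQL score, adjusted for baseline score and the blocking factors actually used. Name those factors, since Section 13 gives only examples. A baseline-adjusted repeated-measures model with the same single contrast is an acceptable alternative.
2. Name one main time point; 12 months fits the longer-term wording of aim iii. Set non-overlapping analysis windows, or a fixed rule assigning each questionnaire to one time point. Say how scores after month 12 are handled, since the synopsis allows them only for the later or reconsented cohort.
3. Keep the ANCOVA as the main analysis in all cases. The unadjusted follow-up comparison, any prevalence analysis (cut-off stated in advance) and any exclusion of post-disclosure baselines are supportive or sensitivity analyses only.
4. State a rule for missing baseline scores, such as the mean of the observed baselines pooled over both arms.
5. Reconcile the synopsis with Sections 4 and 5 so that, for patients still to be enrolled, the baseline questionnaire precedes randomisation and disclosure of the arm.
6. State as a limitation that adjustment does not remove bias in unblinded follow-up reporting.

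The cost is a few sentences in the synopsis, Section 5 and Section 13, with no added patients, visits or questionnaires. The timing change cannot reach patients already enrolled. Naming 12 months accepts fewer patients if follow-up is incomplete, and the gain from ANCOVA may not make up for that. At a correlation of 0.5, ANCOVA with 40 per arm (0.549 SD) still beats the t-test with 50 (0.566 SD). At 0.3 (0.605 SD) it does not.
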